7.9 Visit Windows

It is expected that all visits should occur according to the protocol schedule. All data will be tabulated per the evaluation visit as recorded on the CRF even if the assessment is outside of the visit window. In data listings, the relative day of all dates will be presented.

8 STATISTICAL ANALYSES

8.1 Sample Size Determination

Sample size of 104 randomized 1:1 Active to Vehicle based on 80% power to detect 33% IGA response in Active group versus 10% in the Vehicle group, with two-sided test and $\alpha = 0.05$. Until mentioned all alpha value is set at 0.05.

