4 INVESTIGATIONAL PLAN

4.1 Study Design

- This is a Prospective, Vehicle Controlled, Double Blind, Multicenter, Randomized Phase II trial, Comparing the effect of twice daily B244 application for 8 weeks vs. vehicle application on treatment of mild to moderate rosacea.
- We will enroll approximately 130 subjects and complete 104 subjects.
- At Screening and Baseline:
 - All subjects must have clinical diagnosis of mild to moderate rosacea.
 - Subjects must have IGA score of 2-3 and CEA score of 2-3 in order to qualify for the study.
- After screening and recruitment, participants will be randomized to active or vehicle application for 8 weeks.
- Subjects will apply a total of 4 pumps of IP per application to the face twice-a-day.
- Randomization will be 1:1 B244 to Vehicle.
- Subjects will be provided with cleanser and moisturizer to use for the duration of the study.
- All B244 randomized subjects will be treated at the dose of 4×10^9 cells/ml via spray application.
- Screening will occur at Days -21 to -1.
- Washout will occur after Screening visit (Days -14 to -1).
- Randomization will occur during the baseline visit for the study (Day 1).
- Efficacy will be assessed using Investigator Global Assessment (IGA) score, Clinician’s Erythema Assessment (CEA) score, Patient Self-Assessment (PSA) score and patient reported Skindex 16.
- Clinical assessments of response to treatment will be made at Week 1 (Day 7), Week 4 (Day 28), and Week 8 (Day 56).
- At Baseline visit, subjects will receive a kit containing the drug product. Each bottle will be used for 2 weeks. At Week 4, subjects will return the used bottles from the kit and will be issued a new kit of drug product to be used from Week 4 through Week 8.
- Subjects will stop applying investigational product at Week 8 and will return investigational product at that visit.

- Subjects will come back for a 4-week post-treatment follow up visit at Week 12 (Day 84).
- Participant's safety will be monitored throughout the study. Safety will be assessed by monitoring reported adverse events, vital signs, clinical chemistry and hematology and overall tolerability of the investigational product.
- Subjects would be required to discontinue the investigational product under the following circumstances:
 - Development of an intercurrent illness that would jeopardize the safety, or significantly affect assessments of clinical status of a subject

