14.3 Statistical Analyses

14.3.1 Subject Disposition and Demography

A tabulation of the disposition of subjects will be presented, including the number enrolled, the number randomized, the number treated, and the reasons for study discontinuation. Summaries of the number in each analysis set will be presented. Entry criteria violations and protocol deviations will be listed.

Demographic and baseline characteristic data summarization will be performed in order to descriptively assess the comparability of treatment groups. Data to be tabulated will include age, race, ethnicity, height, weight, and BMI, as well as baseline characteristics related to medical history.

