4.3 Sample Size Considerations

Approximately 130 subjects are planned to be enrolled, and assuming a 20% drop out rate, the planned overall sample size for this clinical trial is approximately 104 adult male and female subjects, 18 years of age and older with mild to moderate rosacea. Subjects will be randomized at a 1:1 ratio (B244: Vehicle) at about 9 clinical research centers in the United States.

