6.4 Data Presentation Conventions

Continuous variables (e.g. age) are summarized using descriptive statistics (the number of subjects with available data, the mean, standard deviation (SD), median, minimum and maximum). Categorical variables (e.g. race) are summarized using counts and percentages. Percentages are calculated using the total subjects per treatment group.

The following conventions are applied to all data presentations and summaries:

- For continuous variables, all mean and median values are formatted to one more decimal place than the measured value. Standard deviation values are formatted to two more decimal places than the measured value. Minimum and maximum values are presented with the same number of decimal places as the measured value.
- For categorical variables, the number and percentage of responses are presented in the form XX (XX.X %) where the percentage is in the parentheses.
- Date variables are formatted as DDMMMYYYY for presentation. Time is formatted in military time as HH:MM for presentation.
- Wherever possible, data will be decimal aligned.
- P-values, if applicable, will be presented to 4 decimal places. If the p-value is less than 0.0001 then it will be presented as <0.0001.

Unless otherwise stated, any statistical tests performed will use 2-sided tests at the 5% significance level.

The table and listing shells and table of contents as part of this SAP provide the expected layout and titles of the tables, listings and figures. Any changes to format, layout, titles, numbering, or any other minor deviation will not necessitate a revision to the SAP nor will it be considered a deviation from planned analyses. Only true differences in the analysis methods or data handling will necessitate such documentation. The appropriate listings supporting the tables will be included and are not specified in the individual sections throughout the document.

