6.7.4 Handling of Missing Data & Sensitivity Analysis

For the primary and secondary analysis no missing values will be imputed. A sensitivity analysis will be performed by Multiple Imputation Regression Analysis using the following factors: treatment, age, gender, race, baseline IGA, baseline CEA, baseline PSA, smokers/non-smokers and the results of the same variable from previous visits.

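### Protocol 14.2 and SAP 8.1 label 104 as the number randomized for 80% power, but the design sections make 104 the number completing out of about 130

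*SAP*

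**What the plan says.** **Power sections.** Protocol 14.2 and SAP v2.0 8.1 carry the same sentence: "Sample size of 104 randomized 1:1 Active to Vehicle based on 80% power". The assumption behind it is "80% power to detect 33% IGA response in Active group versus 10% in the Vehicle group", two-sided, alpha 0.05. The SAP's general convention in 6.4 agrees on sidedness: "any statistical tests performed will use 2-sided tests at the 5% significance level".

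**Design sections.** Protocol 4.1, and SAP 4.1 with it, say "We will enroll approximately 130 subjects and complete 104 subjects". SAP 4.3 gives the link, "Approximately 130 subjects are planned to be enrolled, and assuming a 20% drop out rate", and arrives at a planned overall size of about 104. Protocol 4.2 says the same.

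**Missing data.** SAP 6.7.4, like Protocol 14.3.4, says "For the primary and secondary analysis no missing values will be imputed". There is one exception: Protocol 5.2 and 14.1 and SAP 4.4 and 6.5.4 carry forward the IGA and CEA change for subjects who stop for lack of effect.

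**Test.** SAP 8.3 compares Week 8 success proportions with a continuity-corrected Z-test and classes all efficacy endpoints as exploratory.

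**The concern.** With 20% dropout, 104 cannot be both the number randomized and the number who complete. The two labels also give different power, because most dropouts before Week 8 contribute nothing to an observed-data comparison of proportions.

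The power sentence is the one a study report would quote, and the one a reader would go to for the randomization target. Taken literally, it attaches 80% power to a number that does not deliver it under the plan's own dropout rate. Although efficacy is exploratory, SAP 8.3 plans a superiority test and SAP 6.5.4 treats the mITT result as definitive for superiority. The power figure should therefore be right.

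**Working it through.** **Inputs.** p1 = 0.33, p2 = 0.10, two-sided alpha 0.05, 1:1 allocation, 80% power (Protocol 14.2, SAP 8.1); dropout 20% (Protocol 4.2, SAP 4.3).

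**1. The dropout step reproduces.** 104 / (1 − 0.20) = 130, exactly the planned enrolment. So 104 is the number after dropout.

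**2. The plan's 104 against standard formulas.** With p̄ = (0.33 + 0.10)/2 = 0.215, the pooled formula is

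n per arm = [1.960 × √(2 × 0.215 × 0.785) + 0.842 × √(0.33 × 0.67 + 0.10 × 0.90)]² / 0.23²

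This gives 48.9, so 49 per arm and 98 in total. With the continuity correction it is 58 per arm, 116 in total. Neither gives 104. However, 104 evaluable does exceed 80% for an uncorrected test:

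- 52 per arm, uncorrected: z = (0.23 − 0.1579)/0.0773 = 0.93, power 82.4%.
- 52 per arm, corrected (subtract 1/52 = 0.0192 from the difference): z = 0.68, power 75.3%.

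**3. If 104 is taken as the number randomized.** 104 × 0.80 = 83.2 evaluable, or 41.6 per arm.

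- Uncorrected: z = (0.23 − 0.1766)/0.0865 = 0.62, power 73.2%.
- Corrected (subtract 1/41.6 = 0.0240): z = 0.34, power 63.3%.

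**4. Exact check.** For every pair of response counts, take the binomial probability under 33% and 10%, and add it to the power if the two-sided Z-test rejects in favour of B244. Ranges cover pooled and unpooled standard errors. The second row also covers splits of 42/42, 42/41 and 41/42.

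| Evaluable at Week 8 | Uncorrected Z | Continuity-corrected Z |
|---|---|---|
| 104 (52 per arm) | 84.0–84.5% | 76.3–78.0% |
| 83–84 (41–42 per arm) | 73.9–77.1% | 64.3–68.1% |

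**5. Does the carry-forward rule change this?** At the bound where every dropout stays in the analysis as a non-responder, the rates become 0.33 × 0.80 = 0.264 and 0.10 × 0.80 = 0.080 with 52 per arm. The formula gives 70.6% uncorrected and 60.8% corrected, still below 80%.

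**6. What if some dropout falls after Week 8?** The documents do not say when dropout occurs. As an assumption, let the 20% accrue evenly over 12 weeks: 20% × 8/12 = 13.3% is lost by Week 8, leaving 104 × 0.867 ≈ 90, or 45 per arm. Exact uncorrected power is then 79%. By the formula with the correction, z = (0.23 − 0.0222 − 0.1698)/0.0831 = 0.46, power 67.6%.

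**The case against.** The strongest reply is that the documents already settle the number. The figure of 130 appears repeatedly in both documents, and nothing plans to stop randomization at 104. The power sentence can be read as the same 104, with the next words describing only the allocation ratio. This stands as to intent. It does not make the sentence correct, because its plain wording randomizes 104.

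A reader might infer that the documents leave open whether enrolled subjects are randomized subjects, since Protocol 14.3.1 tabulates disposition "including the number enrolled, the number randomized, the number treated". The rest of the text does not support that doubt. Protocol 6.5 randomizes a subject once eligible and ready for enrollment. Protocol 10.1.2 identifies ineligible subjects before enrollment. SAP Table 14.1.1.3 reports the enrolled count by treatment arm, which presupposes randomization. The 130 are therefore the subjects to be randomized.

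It is also fair to say that 83 evaluable is a lower bound. Some subjects who stop for lack of effect are carried forward, and subjects who leave between Weeks 8 and 12 still have Week 8 data. With even dropout the uncorrected shortfall is only about one point.

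Finally, part of the gap under the corrected test comes from the correction and not from the label: 104 evaluable already gives only 76–78% there. Relabelling alone would not restore 80% for that test.

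**Conclusion.** The point holds as a mislabelled power statement. Protocol 14.2 and SAP 8.1 call 104 the number randomized, while the design sections make it the number left from about 130 after 20% dropout. If 104 were used as the randomization target, with the full 20% lost before Week 8 and no imputation, exact power would be about 74–77% uncorrected or 64–68% continuity-corrected, against the stated 80%.

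A reader might infer that the trial as planned is short of subjects because of this. The documents do not support that: with 130 randomized and 104 evaluable, exact power is about 84% for an uncorrected test. What does remain is that the 80% claim is not met under the continuity-corrected test in SAP 8.3, where 104 evaluable gives about 76–78%.

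These figures rest on the stated response rates and on a two-sided test. The hypotheses in SAP 8.3 are written in one direction, and a one-sided 0.05 uncorrected test would give 82.3% at 41 per arm. However, the power statement and SAP 6.4 both specify two-sided testing. The primary objective is descriptive safety and does not depend on this calculation.

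**What to change.** In Protocol 14.2 and SAP 8.1, replace the label with: *approximately 130 randomized 1:1 (65 per arm) to give about 104 evaluable at Week 8 (52 per arm) after 20% dropout*.

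Replace the stated 80% with the power for 104 evaluable under a named test at two-sided 0.05, 33% versus 10%: about 84% for the uncorrected Z-test, or about 76–78% (exact) for the continuity-corrected Z-test in SAP 8.3. The 80% should not be kept against the corrected test.

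The cost is wording, plus a slightly less favourable stated power if the corrected test is retained. No subjects are needed beyond the 130 already planned. Should the sponsor want 80% under the corrected test, the formula asks for about 116 evaluable, or 116/0.80 = 145 randomized. That is a separate design choice, which this correction does not require.

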8.2 Safety Analysis

Safety analyses will be conducted using the Safety population

8.2.1 Primary Safety Endpoint

Assess the safety and tolerability of B244 applied twice daily to the face for 8 weeks in subjects with mild to moderate rosacea.

The reporting of safety data is descriptive and will include all subjects who receive at least one dose of investigational product. The variables for safety endpoints are number of subjects with AEs, SAEs, vital signs measurements, clinical chemistry and hematology. AEs will be summarized based on the frequency of AEs and their severity for all treated subjects. All AEs will be coded using Medical Dictionary for Regulatory Activities (MedDRA) and summarized by treatment group. Data will be summarized using preferred term and primary system organ class.

If a subject experiences multiple events that map to a single preferred term, the greatest severity and strongest Investigator assessment of relation to investigational product will be assigned to the preferred term for the appropriate summaries. Should an event have a missing severity or relationship, it will be classified as having the highest severity and/or strongest relationship to investigational product.

Summaries of AEs will include any AEs reported beginning with the first dose of investigational product on Day 1. The occurrence of adverse events will be summarized by treatment group using preferred terms, system organ classifications, and severity. Separate summaries of serious adverse events, adverse events related to investigational product, and events leading to the discontinuation of investigational product will be generated. All adverse events reported will be listed for individual subjects showing both verbatim and preferred terms.

8.3 Efficacy Analysis

All efficacy endpoints are exploratory endpoints.

Assessment of Superiority:

- IGA treatment success, defined as “clear” or “almost clear” with a 2-grade improvement in IGA score from baseline to the end of treatment (Week 8).
- CEA treatment success, defined as “clear” or “almost clear” with a 2-grade improvement in CEA score from baseline to the end of treatment (Week 8).

Superiority will be based on the proportion of subjects for whom treatment was successful. The comparison will be through a continuity-corrected Z-tests. The Evaluable Period for the outcome variables will be weeks 1, 4, 8 and 12. The superiority of the drug over the vehicle will be tested at week 8 based on the probability of

improvement from baseline with a continuity-corrected Z-tests comparing the change from baseline of treatments vs Placebo. For all other evaluable periods, descriptive statistics for the change from baseline will be shown.

The null and alternative statistical hypotheses for the primary effectiveness endpoints are given by:

(*H*₀): The null hypothesis is that the probability of improving (baseline to week 8) with drug T (*Pr*_T) is less than or equal to the probability of improving with vehicle (*Pr*_V).

$$H_0: Pr_T - Pr_V \leq 0; Pr_T$$

(*H*_a): The alternative hypothesis is that the probability of improving with drug T (*Pr*_T) is greater than to the probability of improving with vehicle (*Pr*_V).

$$H_a: Pr_T > Pr_V; Pr_T - Pr_V > 0$$

For testing the superiority, the following SAS code will be used:

```
proc freq data = dataset;
  tables treat*outcome/riskdiff (equal);
run;
```

- Change of Skindex 16 patient reported outcome from Baseline to Week 1, Week 4, Week 8 and Week 12

The change from baseline score of Skindex-16 will be compared among treatments at Week 12 using an ANOVA, to test the Skindex 16 score change from Baseline to Week 12 for the two treatments. Also, descriptive stats will be used to assess the change from Baseline to Week 1, 4, 8 & 12.

- Change of IGA score at Baseline to Week 1, Week 4, Week 8 and Week 12.
- Change of CEA score at Baseline to Week 1, Week 4, Week 8 and Week 12.
- Change of PSA score at Baseline to Week 1, Week 4, Week 8 and Week 12.

Descriptive stats will be used to show the change from Baseline to Week 1, 4, 8 & 12.

- Supplemental Analysis
 Supplemental analysis will be performed based on any IGA or CEA improvement from Baseline including p-values for the change from Baseline to Week 8 within each treatment group, and IGA and CEA for the subgroup of patients that had a baseline IGA or CEA of 3.

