14.3.3 Hypothesis Testing/ Assessment of Efficacy

Further details of the planned statistical methods presented below will be provided in the study Statistical Analysis Plan (SAP). The purpose of the SAP is to further elaborate the statistical methods described in the protocol and describe analysis conventions to guide the statistical programming work. Any changes to the final SAP will be documented. Unless otherwise specified, the hypothesis testing will be conducted by the difference of means for a two-sample two-sided test with a significance level of 0.050.

The Evaluable Period for the outcome variables will be weeks 1, 4, 8 and 12. During each Evaluable Period an ordinal value based on IGA, CEA, PSA scores will be collected. The probability of improving will be the criteria to assess the superiority of the drug over the vehicle. The null and alternative statistical hypotheses for the primary effectiveness endpoints are given by:

(*H₀*) : The null hypothesis is that the probability of improving (across the scale) with drug T (*Pr_T*) is less than or equal to the probability of improving with vehicle (*Pr_V*)

$$H_0: PrT \leq PrV; PrT - PrV \leq 0$$

(*H_a*): The alternative hypothesis is that the probability of improving with drug T (*Pr_T*) is greater than to the probability of improving with vehicle (*Pr_V*).

$$H_a: PrT > PrV; PrT - PrV > 0$$

The change from baseline score of Skindex-16 will be compared among treatment at weeks 1, 4, 8 and 12 by a repeated measure analysis.

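### SAP 8.3 rests the Week 8 superiority test on treatment success and also on improvement, and the 33% versus 10% behind the sample size is tied to neither

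*SAP*

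**What the plan says.** SAP v2.0 section 8.3 lists two outcomes under its superiority heading: IGA treatment success and CEA treatment success, each meaning clear or almost clear with a 2-grade improvement at Week 8. It continues: "Superiority will be based on the proportion of subjects for whom treatment was successful". The same paragraph then states the test again: "The superiority of the drug over the vehicle will be tested at week 8 based on the probability of" improvement from baseline, by a continuity-corrected Z-test. The null and alternative hypotheses concern the probability of improving and carry no grade threshold. The SAS code cross-tabulates treatment with a variable named `outcome`, which is not defined.

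Other places point in different directions:

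- Protocol 14.3.3: "The probability of improving will be the criteria to assess the superiority of the drug over the vehicle". Treatment success appears separately in 14.3.3.1, as exploratory and with no test attached.
- The efficacy analysis in the SAP synopsis gives the improvement test only.
- The last item of SAP 8.3 places any IGA or CEA improvement in a supplemental analysis.
- In the table shells, 2-grade improvement (14.2.6.1) and score 0/1 at end of treatment (14.2.8.1) each have a risk difference and p-value. Change by grade (14.2.1.1) has counts only.

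SAP 8.1 and protocol 14.2 base the sample size on "33% IGA response in Active group versus 10% in the Vehicle group". Neither document defines IGA response.

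**The concern.** With entry grades of 2 to 3, success and improvement are different binary outcomes. A programmer who follows the sentence on success and one who follows the hypotheses would code `outcome` differently, and the two tests can disagree on the same data. With both readings in the approved text, the choice could be made after the results are known.

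This matters although efficacy is exploratory, because SAP 6.5.4 treats the mITT result as definitive for superiority and section 8.3 sets out formal hypotheses. The power statement has the same gap: a reader cannot tell which outcome, or which version of the Z-test, the 80% describes.

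**Working it through.** **1. Are the outcomes different?** Entry requires IGA 2-3 and CEA 2-3 (SAP 4.1). Taking a 2-grade improvement as at least two grades, the possible improvements classify as follows.

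| Change | Improvement | Score 0/1 | Success |
|---|---|---|---|
| 3 to 2 | yes | no | no |
| 2 to 1 | yes | yes | no |
| 3 to 1, 3 to 0, 2 to 0 | yes | yes | yes |

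The three outcomes are nested but not the same. A 2-grade improvement always ends at 0 or 1, so Table 14.2.6.1 is the success analysis. Table 14.2.8.1 tests a third, wider outcome.

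**2. Does the stated sample size reproduce?** Inputs from SAP 8.1: 33% and 10%, 1:1 allocation, 80% power, two-sided, and "Until mentioned all alpha value is set at 0.05". The mean rate is (0.33 + 0.10)/2 = 0.215.

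- Pooled normal formula: n = [1.960 × √(2 × 0.215 × 0.785) + 0.842 × √(0.33 × 0.67 + 0.10 × 0.90)]² / 0.23² = (1.139 + 0.469)² / 0.0529 = 48.9, so 49 per arm, N = 98.
- With continuity correction: n' = (n/4) × [1 + √(1 + 4/(0.23n))]² = 57.3, so 58 per arm, N = 116.

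The planned 104 lies between the two and is not returned by either. The dropout step does reproduce: 104/0.8 = 130.

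**3. Power at 52 per arm for 33% versus 10%.** The test statistic is z = (|d| − c)/√(2p̄(1 − p̄)/52), where d is the observed difference, p̄ the pooled proportion, and c = 1/52 with the correction or 0 without. Summing binomial probabilities over all tables with z above 1.960 in favor of B244 gives 84.0% uncorrected and 76.3% corrected. The SAP does not state the variance form; with unpooled variance the corrected figure is 78.0%.

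**4. Power if the rates belong to the other outcome.** This needs the share of improvers who reach success. The documents do not give it, so 75% and 50% are assumed, equal in both arms.

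| 33% v 10% describes | Assumed share | Outcome tested | Rates | Uncorrected | Corrected |
|---|---|---|---|---|---|
| Any improvement | 75% | Success | 24.75% v 7.5% | 68.6% | 57.8% |
| Any improvement | 50% | Success | 16.5% v 5% | 48.5% | 33.9% |
| Success | 75% | Any improvement | 44% v 13.3% | 95% | 92% |
| Success | 50% | Any improvement | 66% v 20% | over 99% | over 99% |

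The rates come from multiplying by the share (0.75 × 33 = 24.75) or dividing by it (33/0.75 = 44).

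**The case against.** The strongest reply is that the SAP largely signals its intention. Only the two success outcomes stand under the superiority heading, any improvement is labelled supplemental, and the shells give no between-arm p-value for any improvement. On that reading the defect is hypothesis wording left unaligned. This is a fair account of what was probably meant, and the fix adopts it. It does not remove the contradiction: the hypotheses, the SAP synopsis and the protocol criterion all name improvement, and the code leaves `outcome` open.

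It also stands that the primary objective is safety and that SAP 8.3 calls all efficacy endpoints exploratory. That limits the consequence.

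Three stronger readings are tempting, and the documents do not support them:

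- **Change from baseline as a third basis for the test.** The phrase is there, but the named Z-test and the risk-difference code compare proportions, and IGA and CEA change is assigned descriptive statistics. It is loose wording.
- **Any improvement reduced to within-arm testing.** The supplemental item says its analysis includes within-group p-values; it does not confine the analysis to them.
- **The 80% can hold for at most one outcome.** If 33% versus 10% is success, both outcomes exceed 80% without the correction (84% for success; 95% or more for any improvement under the assumed shares).

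**Conclusion.** The concern holds. SAP 8.3 states two outcomes for one Week 8 superiority test, so two superiority answers per scale are open. The 33% versus 10% is tied to neither outcome. Under the continuity-corrected test that 8.3 names, power for those rates is about 76% with pooled variance, short of the stated 80%; uncorrected it is 84%.

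A reader might infer that 104 is an error. That is not shown: it gives at least 80% without the correction and somewhat less with it. What is undetermined is which outcome and which test the 80% describes. If the rates are for any improvement, corrected power for success falls to 58% or 34% under the assumed shares. If they are for success, corrected power for any improvement is 92% or more.

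The power figures assume 52 analyzed per arm, that is, 104 completers as in SAP 4.1, and a two-sided 5% level. The point should be corrected, but with efficacy exploratory it does not threaten the primary safety objective.

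**What to change.** 1. In SAP 8.3 and the synopsis, state that superiority at Week 8 in mITT is assessed on treatment success, as already listed under the superiority heading, and say how IGA success and CEA success rank.
2. Delete the wording that rests the same test on the probability of improvement and on change from baseline. Rewrite both hypotheses, and define `outcome` in the code, for the probability of success.
3. Label any improvement and score 0/1 (Table 14.2.8.1) as supportive between-arm comparisons.
4. In SAP 8.1, define IGA response and restate the power for that outcome under the test actually used, with or without the continuity correction.

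The cost is SAP wording, a documented departure from protocol 14.3.3, which names improvement as the criterion, and probably a less favorable stated power. Visits, data collection and treatment do not change.

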3.1.2 Exploratory Objectives

To assess the efficacy of B244 in subjects with mild to moderate rosacea.

- Proportion of subjects with IGA improvement at Week 8 relative to baseline.
- Proportion of subjects with CEA improvement at Week 8 relative to baseline.
- Change in IGA score from Baseline to Week 8.
- Change in CEA score from Baseline to Week 8.
- Proportion of Subjects with improvement in IGA or CEA at Week 1, Week 4, and Week 12.
- Change in Skindex 16 patient reported outcome from Baseline to Week 1, Week 4, Week 8, and Week 12.
- Proportion of subjects with change in PSA at Week 1, Week 4, Week 8 and Week 12 from Baseline.
- Evaluation of Telangiectasia Score at Baseline/Day 1 and Week 8

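### SAP v2.0 section 8.3 has no main between-arm test on the full IGA or CEA scale, although Week 8 change in each score is a stated objective; an ordinal test beside the success comparison is a cheap improvement

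*SAP*

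**What the plan says.** Protocol 11.1.6 and 11.1.7 define IGA and CEA as 0-4 scores, and eligibility requires a score of 2 or 3 on both at Screening and Baseline.

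SAP v2.0 section 8.3 defines treatment success on each scale as clear or almost clear with a 2-grade improvement at Week 8. It says "Superiority will be based on the proportion of subjects for whom treatment was successful", using a continuity-corrected Z-test. The same section also words a Week 8 superiority test on the probability of improvement. For the change scores it says "Descriptive stats will be used to show the change from Baseline to Week 1, 4, 8 & 12".

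Section 3.1.2 nevertheless lists "Change in IGA score from Baseline to Week 8" as an objective, with a matching entry for CEA, separately from the proportions improved. Protocol 14.3.3 words its null hypothesis over the scale: "The null hypothesis is that the probability of improving (across the scale) with drug T".

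The sample size in section 8.1 is "based on 80% power to detect 33% IGA response in Active group versus 10% in the Vehicle group", 104 subjects in all. IGA response is not defined there, and no planning rates are given for CEA.

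Other inferential output in v2.0:
- Table 14.2.8.1 (repeated for CEA): risk difference, CI and p-value for a score of 0/1.
- Supplemental analysis at the end of 8.3: any improvement, with p-values for change within each treatment group, and a baseline grade-3 subgroup.
- Tables 14.2.10.1-3: CI and p-value for change from baseline after multiple imputation, with no analysis model stated.

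**The concern.** Everyone enters at 2 or 3, so a 2-grade fall always ends at 0 or 1. Success is therefore just the change score cut at two grades. Under that cut, a subject who goes from mild to almost clear counts the same as one who does not change or who worsens.

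The other main comparisons move the cut but keep it yes/no. The p-values specified for change in the supplemental analysis are within arm and do not compare B244 with vehicle. The one full-scale p-value sits in a sensitivity shell that has no stated model and no corresponding main analysis. Two stated objectives thus have no specified between-arm test, and no passage gives a reason for leaving out the intermediate grades.

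At 52 per arm the success comparison would rest on about 52 × 0.10 = 5 events against 52 × 0.33 = 17. If the benefit is spread over the scale, the trial could miss an effect that its own data would show.

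**Working it through.** **Inputs from the documents.** 104 subjects 1:1, so 52 per arm; 33% vs 10%; two-sided 0.05 (SAP 8.1 and 6.4).

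**Assumptions.** 33% vs 10% is read as 2-grade success. The documents do not give the other vehicle grades. Nine vehicle distributions were tried, each with 10% at 2 grades better, 5-50% at 1 grade better, 35-80% unchanged and 0-20% worse.

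**Step 1: the plan's own figure.** With d = 0.23 and mean rate 0.215:

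n = [1.96·√(2·0.215·0.785) + 0.842·√(0.33·0.67 + 0.10·0.90)]² / 0.23² = (1.139 + 0.469)² / 0.0529 ≈ 48.9

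This gives 49 per arm, 98 in all. With the Fleiss continuity correction it is 58 per arm, 116 in all. The stated 104 lies between the two. No formula is given, so it is not reproduced exactly and is not called wrong. The enrolment figure does follow: 104 / 0.80 = 130.

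**Step 2: power of the 2-grade comparison at 52 per arm** (exact enumeration).
- Uncorrected pooled Z: 84.0%.
- Corrected by 1/52: 76.3% (pooled variance) or 78.0% (unpooled).

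**Step 3: power on the full change score.** The odds ratio at the 2-grade cut is (0.33/0.67)/(0.10/0.90) = 4.43; the equivalent latent-normal shift is 0.84 SD. That effect was applied at every cut, and a tie-corrected Wilcoxon test was simulated 20,000 times per scenario on four categories (worse, 0, 1, 2 or more grades better).
- Over nine distributions and both shift models: 92.5-98.5%.
- Example, vehicle 10/30/50/10% (2 grades, 1 grade, none, worse): 98.1% (common odds), 97.3% (latent normal).
- Van Elteren stratified by baseline grade, with 30, 50 or 70% entering at grade 2: about 97%.

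Gain over the uncorrected test: 92.5 − 84.0 = 8.5 to 98.5 − 84.0 = 14.5 points. Gain over the corrected test: 92.5 − 78.0 = 14.5 to 98.5 − 76.3 = 22.2 points.

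**Step 4: the any-improvement comparison in 8.3.** Under a common odds ratio of 4.43 (for example, vehicle 40% gives odds 0.667 × 4.43 = 2.96, so B244 75%):

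| Vehicle any improvement | B244 | Any-improvement Z, uncorrected / corrected | Rank test |
|---|---|---|---|
| 30% | 66% | 97% / 95% | 98% |
| 40% | 75% | 96% / 94-95% | 98% |
| 50% | 82% | 94% / 90-91% | 98% |

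The gain is about 1-4 points uncorrected and 3-7 corrected. Over all nine distributions the gain on the corrected test widens to about 3-13 points (common odds) and 5-15 (latent normal).

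If the true common odds ratio is 2.5 and vehicle any-improvement is 40%, power is about 70% (rank), 67% / 60% (any improvement, uncorrected / corrected) and 37% / 27% (2-grade).

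**Step 5: when the effect is not a common shift.** Keep 33% vs 10% at the 2-grade cut and shrink the log odds ratio at the lower cuts:

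| Lower-cut log odds ratio as a fraction of that at 2 grades | Rank test | 2-grade Z, uncorrected |
|---|---|---|
| 1 | 98% | 84% |
| 0.75 | 90-92% | 84% |
| 0.5 | 67-76% | 84% |
| 0.25 | 35-48% | 84% |

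Break-even is near 0.60-0.65. In the extreme, with vehicle 10/30/50/10 and all extra successes taken from 1-grade improvers, the rank test has 14% power; if they come only from non-improvers, 73%.

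**Step 6: other readings.** If IGA response means any improvement (33% vs 10% at 1 grade or more), the rank test has 90-94% against 84%. At 65 per arm (no dropout), the 2-grade test has 91% uncorrected or 87% corrected, and the full-scale test 97-99.6%.

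**The case against.** The strongest reply is that the SAP is not confined to 2-grade success. Section 8.3 also words a test on improvement, Table 14.2.8.1 gives a p-value for a score of 0/1, and the supplemental analysis covers any improvement. A grade-2 entrant who reaches almost clear counts in all three. Table 14.2.1.1 reports 1-, 2- and 3-grade changes by arm, so intermediate grades are still displayed. This stands. A reader might infer that 2-grade success is the only between-arm comparison; the documents do not support that. What remains is that none of the main comparisons uses the full scale.

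Second, a reader might infer one fixed loss of 13 or 14 points from the plan's own 33% vs 10%. The documents do not support that either. IGA response is undefined, and Amendment 3 added 2-grade success with no sample-size change in its summary. The intermediate grades are unknown, and the loss shrinks to a few points once any improvement is the comparator.

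Third, protocol 14.3.3 might be read as requiring a test of means. Its difference-of-means default applies only where nothing else is specified, and the section then makes the probability of improving the criterion. A responder comparison is consistent with the protocol.

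Finally, efficacy is exploratory and there is no multiplicity correction, so this adds one more unadjusted p-value per scale. That limits the weight of the point but does not give the two change objectives an analysis.

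**Conclusion.** The point holds as a gap in specification with a modest, conditional cost. Week 8 change in IGA and in CEA are stated objectives with no main between-arm test.

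If 33% vs 10% is 2-grade success and the effect is a common shift, the full-scale test gains about 8-14 points over the uncorrected 2-grade test and 14-22 over the corrected one. Over the any-improvement comparison the gain is about 1-7 points under a common odds ratio of 4.43 with vehicle any-improvement of 30-50%. The rank test loses to the uncorrected 2-grade test once the lower-cut log odds ratio falls below roughly 0.6 of that at the 2-grade cut, so it should be added and should not replace the success comparison. For CEA these sizes are borrowed from the IGA planning rates.

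This is a cheap improvement to an exploratory analysis. It is not a flaw in the primary safety objective or evidence that the responder analysis is wrong.

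**What to change.** In SAP section 8.3, before unblinding:

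1. Name a two-sided 0.05 between-arm van Elteren test of Week 8 change in IGA and in CEA, in the mITT, stratified by the baseline grade of the same scale, as the analysis of the two change objectives.
2. Report with it a proportional-odds common odds ratio, adjusted for baseline grade, with 95% CI.
3. Add the p-value and odds-ratio rows to the Week 8 block of Tables 14.2.1 and 14.2.2.
4. Keep the 2-grade success comparison, with its risk difference and CI, unchanged beside it.

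Cost: SAP wording and a few lines of code; no new data or subjects. Downsides: one more exploratory p-value per scale, an odds ratio that is less direct to read than a responder rate, and less power than the success test if the benefit is concentrated in 2-grade responders.
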